9.2. Sample Size Determination

Approximately 270 participants will be randomized (2:1:2) to receive placebo, 0.3 mg JZP150, or 4 mg JZP150. Participants will be stratified by the presence or absence of concomitant use of SSRIs/SNRIs.

The sample size was determined based on ensuring at least 80% marginal power to detect a difference of 6 between placebo and each dose of JZP150 for the mean change in CAPS-5 total symptom severity score from Baseline to Week 12. The sample sizes for the estimated 70% of subjects completing the 12-week dosing period for each arm (placebo [n = 75], 0.3 mg JZP150 [n = 38], and 4 mg JZP150 [n = 75]) provides a marginal power of 80.9% and 93.4% for comparing the low dose vs placebo and high dose vs placebo, respectively. Calculations are based on assuming a common standard deviation of 10.5, using a two-sample t-test, and two-sided significance level of 0.05. To account for a 30% dropout, the sample size will be 270 participants to ensure that a minimum of 188 participants have 12 weeks of treatment data.

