5.4. Randomization and Blinding

All participants who sign the informed consent form (ICF) will receive a participant number. The participant number identifies the participant for all study procedures that occur throughout the study. This number is unique and once assigned cannot be reassigned to another study participant.

Treatment allocation/randomization for this study will occur centrally through the use of an interactive response technology (IRT). Following screening, eligible participants will be randomized (2:1:2) to one of three treatment arms: placebo, JZP150 0.3 mg QD, or JZP150 4 mg QD. Randomization will be stratified based on presence versus absence of use of a stable SSRI/SNRI at Screening. The sponsor, CRO, study investigators, clinical raters, and participants will be blinded to treatment assignment.

A double-blind approach will be used throughout the 12-week treatment period. During the study, the number of capsules taken each day will be the same for participants randomized to each treatment, and JZP150 and placebo capsules will look and feel identical.

The IRT will be programmed with blind-breaking instructions. In case of an emergency, the investigator has the sole responsibility for determining if unblinding of a participant's intervention assignment is warranted. Participant safety must always be the first consideration in making such a determination. If the investigator decides that unblinding is warranted, the investigator should make every effort to contact the sponsor prior to unblinding a participant's intervention assignment unless this could delay emergency treatment of the participant. If a participant's intervention assignment is unblinded, the sponsor must be notified within 24 hours after breaking the blind. The date and reason(s) that the blind was broken must be recorded in the source documentation and case report form, as applicable. The participant's treatment assignment may be unblinded for regulatory reporting purposes. Notification of the treatment assignment is only made known to those who require it for safety reporting and submission processes. All other individuals involved in the study, including the investigator (with the

Jazz Pharmaceuticals
 {Statistical Analysis Plan - Protocol #}JZP150-201-02

exception noted above), will remain blinded to treatment assignment. Participants for whom the blind is broken for this reason will not be withdrawn from the study.

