9.2.6.1. Responder Analysis

The responders are defined in 3 ways in [Section 4.2.3](#). Three separate responder analyses will be performed for the CAPS-5 total score, CGI-C, and PGI-S responders. Missing data will not be imputed for responder analysis.

The CGI-C is a 7-point Likert-type rating scale widely used to assess efficacy in clinical drug trials ([Guy 1976](#)). Investigators or trained raters will rate their impression of any change in the severity of the participant's condition since Baseline on a 7-point scale ranging from 1 (very much improved) to 7 (very much worse). Ratings will focus on the participants' change in their ability to function due to PTSD. CGI-C is assessed at end of Weeks 4 and 12. The CGI-C responder analysis will be performed for Week 4 and Week 12 separately.

In each responder analysis, the proportion of participants will be compared between each dose of JZP150 and placebo using the Cochran-Mantel-Haenszel (CMH) test stratified by randomization stratum. The point estimate and continuity corrected Wilson's 95% CI (as modified by Newcombe) for the difference of the proportion will also be provided.

Example SAS Code for obtaining the CMH test p-value, point estimate and 95% CI for the difference in proportion is provide below:

```
PROC FREQ DATA=ANAL;
  TABLES STRATUM*TRT*RESPONDER1/CMH;
  RUN;
```

Jazz Pharmaceuticals
 {Statistical Analysis Plan - Protocol #}JZP150-201-02

```
PROC FREQ DATA=ANAL;
TABLES TRT*RESPONDER1/RISKDIFF(CL=(WILSON(CORRECT)));
RUN;
```

9.2.6.2. CAPS-5 total score change from Baseline to Week 4

The CAPS-5 total score is described in [Section 9.1.1](#). The results for the change in the CAPS-5 total score from Baseline to Week 4 will be presented using the Week 4 contrasts of the MMRM modeling results for the primary endpoint (the CAPS-5 total score from Baseline to Week 12). The modeling details are described in [Section 9.1.2](#).

9.2.6.3. Change in B-IPF and SDS from Baseline to Week 12.

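### Responder p-values are stratified and uncorrected, but the response difference and its 95% CI are unstratified and continuity-corrected, so the CI over-covers and can include 0 beside p<0.05

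*SAP*

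**What the plan says.** SAP 9.2.6.1 covers three responder definitions: CAPS-5 at Week 12, CGI-C at Weeks 4 and 12, and PGI-S at Week 12. Each is compared between each dose and placebo, which makes four analyses per dose.

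- **Test.** The comparison is made "using the Cochran-Mantel-Haenszel (CMH) test stratified by randomization stratum". The example code is "TABLES STRATUM*TRT*RESPONDER1/CMH", with no continuity correction.
- **Estimate and interval.** The text says "The point estimate and continuity corrected Wilson's 95% CI (as modified by Newcombe) for the difference of the proportion will also be provided". It does not mention the stratum. The code is "TABLES TRT*RESPONDER1/RISKDIFF(CL=(WILSON(CORRECT": a two-way table without STRATUM, with the correction switched on.
- **Stratum.** SAP 5.4: "Randomization will be stratified based on presence versus absence of use of a stable SSRI/SNRI at Screening".
- **Missing data.** "Missing data will not be imputed for responder analysis".

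SAP 9.2.6 rules out sensitivity and supplementary analyses for these endpoints, so no stratified responder estimate appears elsewhere.

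**The concern.** A p-value and a confidence interval printed on the same row should come from compatible methods. Here the test conditions on the stratum and is uncorrected, while the interval ignores the stratum and is deliberately widened. Two consequences follow. The nominal 95% interval covers more than 95%. And the table can show p<0.05 beside an interval that includes 0.

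Protocol Section 3 makes the difference in proportions the population-level summary for responder endpoints, so the interval is the reported effect and not decoration. The pairing is also out of line with the SAP's continuous endpoints, where the MMRM and ANCOVA models put the randomization stratum into the model that yields the estimate.

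**Working it through.** **1. Design figure.** Protocol 9.2 fixes the arm sizes for CAPS-5: "at least 80% marginal power to detect a difference of 6 between placebo and each dose of JZP150"; "Calculations are based on assuming a common standard deviation of 10.5, using a two-sample t-test, and two-sided significance level of 0.05". With n = 75/75 and 38/75, a noncentral-t calculation gives 93.5% and 81.2% (stated: 93.4% and 80.9%), and 188/0.70 = 269 (stated: about 270). The design reproduces. The documents state no response rate, power or interval width for responders.

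**2. Formulas.** Take x1/n1 on active and x0/n0 on placebo.
- CMH: chi-square = [Σ(x1 − E)]² / ΣV, with t = x1 + x0, N = n1 + n0, E = n1·t/N and V = n1·n0·t·(N − t) / [N²(N − 1)] in each stratum.
- Newcombe: lower = d − √[(p1 − l1)² + (u0 − p0)²], upper = d + √[(u1 − p1)² + (p0 − l0)²], where l and u are Wilson limits, with or without continuity correction.
- Mantel-Haenszel (MH) difference: Σw·d / Σw with w = n1·n0/N, using the Sato variance.

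**3. Effect of the correction alone** (one stratum, 48/75 v 36/75, d = 0.160).
- Test: E = 42, V = 9.302, chi-square = 6²/9.302 = 3.870, p = 0.049.
- Corrected Wilson limits: 0.520 to 0.745 and 0.364 to 0.598. Lower = 0.160 − √(0.1197² + 0.1176²) = −0.008. Upper = 0.160 + √(0.1053² + 0.1156²) = 0.316.
- Uncorrected: 0.001 to 0.308.

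The planned interval includes 0. Without the correction it does not.

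**4. Two-stratum examples.**
- 0.3 mg, strata 8/13 v 10/25 and 15/25 v 20/50 (total 23/38 v 30/75). CMH: (1.842 + 3.333)² / (2.190 + 4.204) = 4.189, p = 0.041. Planned CI −0.003 to 0.391; uncorrected 0.011 to 0.378. MH: weights 8.553 and 16.667, difference 5.175/25.219 = 0.205, CI 0.014 to 0.396.
- 4 mg, strata 8/25 v 3/25 and 34/50 v 27/50 (total 42/75 v 30/75). CMH: 6.0² / (2.189 + 6.008) = 4.392, p = 0.036. Planned CI −0.009 to 0.317; uncorrected 0.0004 to 0.309; MH 0.013 to 0.307.

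**5. Simulation** (200,000 trials per scenario). Assumed: 65% v 45% response, 25-40% SSRI/SNRI users, stratum response gap 0, 15 or 30 points, evaluable numbers as in Protocol 9.2. A conflict is a CI that includes 0 among results with CMH p<0.05. A reverse conflict is p≥0.05 with a CI excluding 0, as a share of all trials.

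| n | Interval | Coverage | Mean width | Conflict | Reverse |
|---|---|---|---|---|---|
| 75/75 | Planned | 96.4-97.2% | 0.321 | 5-9% | 0 |
| 75/75 | Unstratified, uncorrected | 94.6-95.7% | 0.303 | 0-0.9% | 0-2.3% |
| 75/75 | MH, Sato | 94.5-94.7% | 0.295-0.310 | ≤0.04% | 0.4-2.3% |
| 38/75 | Planned | 96.5-97.4% | 0.387 | 11-21% | 0 |
| 38/75 | Unstratified, uncorrected | 95.0-96.1% | 0.361 | 0.3-9.9% | ≤0.2% |
| 38/75 | MH, Sato | 94.2-94.3% | 0.356-0.373 | ≤0.05% | 2.5-4.6% |

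Width ratios, planned to uncorrected: 0.321/0.303 = 1.06 and 0.387/0.361 = 1.07. At 108/108, with lower assumed placebo response (30-40%), the ratio is 0.269/0.256 = 1.05.

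**6. Source of the excess.** At gaps of 0 to 15 points, dropping the correction alone removes most of the conflict. At 30 points it still leaves up to 9.9% at 38/75. At an assumed gap of 40 points, the uncorrected unstratified interval covers 96.2-97.0% and is about 4-9% wider than the MH interval.

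**The case against.** The strongest reply is that the continuity correction is written into the text, so it is a deliberate and cautious choice. Randomization is stratified, so arms should be roughly balanced within strata, and a crude difference estimates the protocol's summary directly. These are nominal p-values outside the hierarchy, and the mismatch never made the planned CI exclude 0 when p≥0.05. All of that stands and limits the weight of the point. It does not justify pairing a widened interval with an uncorrected stratified test, for which the SAP gives no reason.

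Three stronger readings should be resisted.

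- **That the code tests the wrong hypothesis because TRT has three levels.** Neither call shows a subset to two arms, so a reader might infer an overall three-arm test. But the text says each dose is compared with placebo, the code is labelled as an example, and the SAP does not say that its generic input dataset holds all three arms. At most, the SAP could add that the code is run on the two arms being compared.
- **That ignoring the stratum is the main fault.** At small stratum gaps nearly all the extra width is the correction. Nor does any stratified interval cure the problem: an MH-weighted stratified Newcombe interval still conflicted with p in 3.9-7.7% of significant results at 38/75 with a 30-point gap.
- **That the unstratified point estimate is biased.** The documents do not show this. It can differ from the stratified estimate if missing responder data unbalance the strata, but nothing indicates by how much.

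**Conclusion.** The point holds as an internal inconsistency in how responder results are reported. Under the assumed rates, the planned 95% CI covers about 96.4-97.4% and is 6-7% wider than the same interval without the correction. It includes 0 in about 5-9% of significant 4 mg results and 11-21% of significant 0.3 mg results. Readers may therefore see a contradictory row; it is not certain that they will.

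These sizes rest on response rates, an SSRI/SNRI share and a stratum gap that the documents do not give. The direction does not rest on them: the correction can only widen the interval. The primary and key secondary analyses and the control of type I error are untouched.

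**What to change.** In SAP 9.2.6.1, for each dose versus placebo, report the Mantel-Haenszel risk difference stratified by randomization stratum, with its matching uncorrected stratified 95% CI (for example the MH interval with Sato variance). In code, this means requesting the common risk difference with MH limits in the existing stratified CMH call, and deleting the unstratified, continuity-corrected RISKDIFF call. Add that the data are limited to the two arms being compared.

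The cost is one sentence and one line of code, and no new data. There is a small statistical price. At the 0.3 mg arm size the MH interval covers about 94%, and it excludes 0 with p just above 0.05 in 2.5-4.6% of simulated trials. The planned interval conflicts in the other direction in roughly 6-12% of trials there (11-21% of the 51-57% that are significant). If the team prefers the smallest edit, dropping only the correction removes most of the problem unless SSRI/SNRI use strongly predicts response. If the corrected interval is kept, the SAP should give the reason and warn that it may include 0 when the CMH p-value is below 0.05.

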9.2.6.7. Change in CAPS-5 Subscales from Baseline

The 4 CAPS-5 subscales are described in [Section 9.1.1](#).

Change in PTSD symptom clusters (intrusive symptoms, avoidance symptoms, arousal/reactivity symptoms, and negative alterations in mood and cognition) as assessed by the change in the 4 CAPS-5 subscale scores from Baseline to Weeks 4 and 12, will be analyzed using an MMRM model, for each of the subscales separately.

The model will include randomized treatment group, corresponding CAPS-5 subscale score at Baseline, week (as a discrete factor), treatment by week interaction, baseline by week interaction, and randomization stratum as fixed effects, and week as a repeated effect. An unstructured variance-covariance matrix will be used to model the correlation among repeated measurements. The modeling detail and SAS code are similar to [Section 9.1.2](#).

9.2.6.8. Change in PHQ-9 from Baseline to Weeks 1, 4, 12 and change in SIGH-A from Baseline to Weeks 4, 8, 12

The PHQ-9 is a component of the longer Patient Health Questionnaire and is a participant-reported tool for assessing depression in the last 2 weeks. The PHQ-9 score is derived from the 9 questions that are rated on a 4-point scale from 0 (Not at all) to 3 (Nearly every day). The PHQ-9 score ranges from 0 to 27 and is assessed at Baseline and end of Weeks 1, 4, and 12.

The SIGH-A is a 14-item clinician administered rating scale developed to measure the severity of anxiety symptoms in the past week or since last visit. The SIGH-A score is derived from the 14 items that are rated on a 5-point scale from 0 (Absent) to 4 (Very severe). The SIGH-A score ranges from 0 to 56 and is assessed at Baseline and end of Weeks 4, 8, and 12. The SIGH-A baseline version is administered at Baseline and the SIGH-A since last visit version is administered at end of Weeks 4, 8, and 12.

[figure not shown]
Change in mood and anxiety as assessed by the change in the PHQ-9 total score from Baseline to Weeks 1, 4, 12 and the change in the SIGH-A total score from Baseline to Weeks 4, 8 and 12, will be analyzed using an MMRM model, separately for PHQ-9 and SIGH-A. The model will include randomized treatment group, corresponding score at Baseline, week (as a discrete factor), treatment by week interaction, baseline by week interaction, and randomization stratum as fixed effects, and week as a repeated effect. An unstructured variance-covariance matrix will be used to model the correlation among repeated measurements. The modeling detail and SAS code are similar to [Section 9.1.2](#).

9.2.6.9. Change in ReQoL from Baseline to Week 12

The ReQoL-10 is a 10-item participant reported outcome that has been developed to assess the quality of life for people with different mental health conditions in the past week. The ReQoL-10 score is derived from the 10 items that are rated on a 5-point scale from 0 to 4. Higher scores indicate better quality of life. The ReQoL-10 score ranges from 0 to 40 and is assessed at Baseline and end of Week 12.

Change in quality of life as assessed by the ReQoL-10 score from Baseline to Week 12 will be analyzed using an ANCOVA model. The model will include randomized treatment group, randomization stratum, and ReQoL-10 score at Baseline as covariates. The modeling detail and SAS code are similar to [Section 9.2.6.3](#).

Jazz Pharmaceuticals
{Statistical Analysis Plan - Protocol #}JZP150-201-02

Jazz Pharmaceuticals
 {Statistical Analysis Plan - Protocol #}JZP150-201-02

10. SAFETY

Safety data will be primarily summarized by treatment group and pooled JZP150 treatment group using the Safety Analysis Set. Summaries of exposure data, AEs, SAEs, laboratory assessments, vital signs, physical examination, and concomitant medications will be presented. Data listings will also be presented for all safety endpoints.

10.1. Exposure

10.1.1. Extent of Exposure

The exposure information will be summarized by treatment group with the Safety Analysis Set and by randomized treatment group with the Full Analysis Set 2 and PK Analysis Set using descriptive statistics as well as counts and percentages, as appropriate. Exposure summaries are based on data collected by the study intervention administration eCRF and data captured in EDC. A listing of study intervention exposure will also be presented.

Duration of exposure, in days, is calculated as: date of last dose of study intervention – date of first dose of study intervention + 1. Interruptions are not taken into account for the duration of exposure.

10.1.2. Treatment Compliance

Summary statistics for compliance to study intervention will be presented using descriptive statistics based on the Safety Analysis Set and Full Analysis Set 2 by treatment group. Compliance will also be summarized by category (<75%, $\geq 75\%$ to $\leq 100\%$, $> 100\%$ to $\leq 125\%$, and $> 125\%$). A listing of compliance will also be presented.

Compliance will be calculated as the number of capsules consumed (data captured in IRT) divided by the number of capsules that should have been consumed by the participant (data captured in EDC), expressed as a percentage i.e.

$$\text{compliance}(\%) = \frac{\text{number of capsules consumed}}{\text{number of capsules that should have been consumed}}$$

10.2. Adverse Events

Adverse events (AEs) occurring from the first dose of study intervention until the final study visit will be reported. If the Investigator becomes aware of an SAE within 14 days after the last dose of study intervention, the event must also be reported. In addition, any SAE assessed as related to study intervention or procedure by the Investigator must be reported regardless of time after study termination.

Adverse events will be coded to SOC and PT using MedDRA, Version 24.0 or later. The investigator will assess the relationship of each AE to study intervention. An AE with a missing relationship to study intervention will be reported as related in the summaries. Severity, as determined by the Investigator, will be classed as mild, moderate, severe, life-threatening, or fatal.

Note that participants who acquire COVID-19 or report AEs due to the COVID-19 public health emergency (e.g., anxiety) while on study will be coded accordingly and included in the treatment emergent adverse event (TEAE) summaries.

Jazz Pharmaceuticals
 {Statistical Analysis Plan - Protocol #}JZP150-201-02

A TEAE is generally defined as any event with onset date on or after the first dose of study intervention, including AEs that occur until 14 days after the last dose date. Any AEs reported 14 days after the last dose date will not be considered treatment emergent and will be included in the listing but not analyzed in the summaries.

For the purpose of calculating treatment emergence, incomplete onset dates will be imputed as detailed in [Appendix 2](#).

For the summary of TEAEs in Safety Analysis Set by time of first onset, data will be summarized under the following categories:

- Week 1 (Day 1 to 7).
- Weeks 2 to 4 (Day 8 to 28).
- Weeks 5 to 8 (Day 29 to 56).
- Weeks 9 to 12 (Day 57 to 84).
- After last dose.

The time of first onset will be calculated for TEAEs as:

$$\text{Start date of TEAE} - \text{Date of first dose of study intervention} + 1 \text{ day}$$

If patients have multiple occurrences of a TEAE then it will be counted once for the first occurrence only. For participants who discontinue study intervention prior to study completion, all TEAEs occurring after treatment discontinuation will be reported in the “After last dose” category.

The time of first onset will also be used to assign TEAEs by study period onset as follows:

- Intervention Period (Day 1 to Day 84 for intervention completers or Day 1 to last dosing day for participants who discontinue intervention early)
- Safety Follow-up Period (> Day 84 for intervention completers or > last dosing day for participants who discontinue intervention early)

If patients have multiple occurrences of a TEAE then it will be counted once for the first occurrence only. For participants who discontinue study intervention prior to study completion, TEAEs occurring after treatment discontinuation will be reported according to the time of first onset.

Only TEAEs are included in summary tables unless otherwise specified. If a participant has multiple episodes of events coded to the same SOC or PT, then the participant will be counted just once in the summaries for that term. For summary tables, participant incidence of TEAEs by SOC and PT are sorted by descending order of frequency of SOC in the JZP150 4 mg treatment arm (then alphabetically for ties) and then by descending order of frequency of PTs within each SOC (then alphabetically for ties). For summaries by PT only, PTs will be sorted in descending order of frequency in the JZP150 4 mg treatment arm. Each TEAE will be summarized by treatment group and pooled JZP150 treatment groups.

For the summary of TEAEs by maximal severity, for each participant, the worst severity recorded by PT and SOC will be used for summary purposes. If severity is missing, the severity level of “severe” will be assumed.

Jazz Pharmaceuticals
{Statistical Analysis Plan - Protocol #}JZP150-201-02

A general overall summary of TEAEs with the number and percent of participants who experienced the following types of events will be provided by treatment group and pooled JZP150 treatment groups:

- Participants with any TEAE
- Participants with any treatment-related TEAE
- Participants with any serious TEAE
- Participants with any treatment-related serious TEAE
- Participants with TEAE by maximum severity
- Participants with an AE outcome as death
- Participants with any TEAE leading to study intervention discontinuation
- Participants with any TEAE leading to study intervention dose interruption
- Participants with at least one TEAE outcome

Participant incidence of TEAEs by SOC and PT will be summarized by treatment group and pooled JZP150 treatment groups for the following:

- TEAEs (by SOC and PT and PT only)
- TEAEs reported in $\geq 2\%$ of participants
- Treatment-related TEAEs
- Serious TEAEs
- Treatment-related serious TEAEs
- TEAEs by maximum severity
- TEAEs leading to study intervention discontinuation
- TEAEs of special interest (by category [defined in [Section 10.2.1](#) and PT])
- TEAEs leading to study intervention dose interruption
- TEAEs by study period onset
- TEAEs by time of first onset

Separate AE listings will be provided including the following:

- All AEs
- AEs with an outcome of death
- SAEs
- AEs leading to permanent withdrawal of study intervention
- Adverse events of special interest (defined in [Section 10.2.1](#))

Jazz Pharmaceuticals
 {Statistical Analysis Plan - Protocol #}JZP150-201-02

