8.4.1. Time Period and Frequency for Collecting AE and SAE Information

All AEs and SAEs will be collected from the start of intervention until the follow-up visit at the time points specified in the SoA ([Section 1.3](#)).

All SAEs that occur after the consent form is signed but before study intervention/treatment must be reported by the investigator if they cause the participant to be excluded from the trial, or are the result of a protocol-specified intervention, including but not limited to washout or discontinuation of usual therapy, diet, placebo treatment, or a procedure.

Medical occurrences that begin before the start of study intervention but after obtaining informed consent will be recorded as Medical History/Current Medical Conditions, not as AEs.

All SAEs will be recorded and reported to the sponsor or designee immediately and within 24 hours of first knowledge of the event by study personnel, as indicated in [Appendix 4](#). The investigator will submit any updated SAE data to the sponsor within 24 hours of it being available.

Investigators are not obligated to actively seek information on AEs or SAEs after conclusion of the study participation. However, if the investigator learns of any SAE, including a death, at any time after a participant has been discharged from the study, and he/she considers the event to be reasonably related to the study intervention or study participation, the investigator should promptly notify the sponsor.

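### SAP 10.2 ends the on-treatment period for completers at Day 84 instead of at last dose, and its two adjacent TEAE sentences run on different clocks

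*SAP*

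**What the plan says.** **Period and onset tables.** SAP 10.2 assigns each TEAE to a study period by its time of first onset. The first period is "Intervention Period (Day 1 to Day 84 for intervention completers or Day 1 to last dosing day for participants who discontinue intervention early". The second is "Safety Follow-up Period (> Day 84 for intervention completers", or after the last dosing day for those who stop early. A separate table groups TEAEs by time of first onset. Its last dated category is "Weeks 9 to 12 (Day 57 to 84", followed only by a category for onset after last dose. For participants who stop study intervention early, "all TEAEs occurring after treatment discontinuation will be reported in the" latter category. There is no matching sentence for completers.

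**TEAE definition.** The same section defines a TEAE by onset on or after first dose, "including AEs that occur until 14 days after the last dose date". The next sentence reads "Any AEs reported 14 days after the last dose date will not be considered treatment emergent", and adds that such events "will be included in the listing but not analyzed in the summaries".

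**Timing.** The schedule in Protocol 1.3 and SAP Table 3 puts the Week 12 visit at Day 84 with a window of -5/+2 days. Protocol 8.1.6 has participants dose in clinic on visit days other than Week 8, and Protocol 8.5 takes predose and postdose samples at Week 12. The safety follow-up visit is 14 days after last dose with a window of +5 days (Protocol 1.3), shown as Day 98 (+5) in SAP Table 3. Protocol 8.4.1 states: "All AEs and SAEs will be collected from the start of intervention until the follow-up visit".

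**The concern.** The period and onset tables are there to separate events on drug from events after it stops. A calendar cut at Day 84 does this only for a completer whose last dose falls on Day 84, and the visit window allows seven other days. For those participants the tables can place an on-drug event in follow-up or a post-drug event in treatment, and the onset categories either leave a gap or overlap.

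The two TEAE sentences raise a separate problem. The first goes by when the event began and the second, as worded, by when it was reported. The safety visit is never scheduled before post-dose day 14, so the two rules can disagree about the same event. TEAE status decides whether an event enters the summary tables at all, so a programmer should not have to choose between them.

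**Working it through.** **Check of the plan's own visit days.** Week 12 is Day 84. The safety visit is 84 + 14 = Day 98, and 98 + 5 = Day 103 at the latest. This agrees with Day 98 (+5) in SAP Table 3.

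**Step 1: range of last-dose days.** Assume that a completer takes the last dose on the Week 12 visit day, within the permitted window. The last dose then falls between 84 - 5 = Day 79 and 84 + 2 = Day 86.

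**Step 2: apply the Day 84 rules.** For last dose on Day L:
- on-drug days assigned to Safety Follow-up are those after Day 84 and up to L, so max(0, L - 84) days;
- post-dose days assigned to Intervention are those after L and up to Day 84, so max(0, 84 - L) days;
- an on-drug day after Day 84 is neither in Days 57 to 84 nor after last dose, so it has no onset category;
- a post-dose day up to Day 84 is both in Days 57 to 84 and after last dose, so it has two.

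| Last dose (study day) | On-drug days put in Safety Follow-up, with no onset category | Post-dose days put in Intervention, with two onset categories |
|---|---|---|
| 79 | 0 | 5 (Days 80-84) |
| 80 | 0 | 4 (Days 81-84) |
| 81 | 0 | 3 (Days 82-84) |
| 82 | 0 | 2 (Days 83-84) |
| 83 | 0 | 1 (Day 84) |
| 84 | 0 | 0 |
| 85 | 1 (Day 85) | 0 |
| 86 | 2 (Days 85-86) | 0 |

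The right-hand column applies only if a participant with a last dose on Days 79 to 83 is an intervention completer. SAP 8.2 requires receipt of 12 weeks of study intervention and does not say whether a visit early in the window meets that. If it does not, the early-discontinuation rule applies, the boundary is the last dosing day, and the count is 0.

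**Step 3: the two TEAE sentences.** The safety visit falls on post-dose days 14 to 19, six permitted days. If the exclusion is read literally as reporting on or after day 14, it catches what is first told on 6 of the 6 days. If it is read as after day 14, it catches 5 of the 6. Take an event with onset on post-dose day 3, first told at a visit on day 15. By onset, 3 ≤ 14, so it is a TEAE. By reporting, 15 > 14, so it is not. An onset on day 14 itself, reported the same day, is also claimed by both sentences.

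**Step 4: after the correction.** With the boundary at L for everyone, both columns of the table become 0. With the exclusion worded as onset more than 14 days after last dose, every onset from day 0 to day 14 after last dose is a TEAE whenever it is reported. For L from 79 to 86, the last TEAE onset day is L + 14, so Day 93 to Day 100.

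**The case against.** A reader might infer that events told at the safety visit will drop out of the tables. The documents do not support that as the intended outcome. The TEAE definition goes by onset. The SAP imputes incomplete onset dates expressly to determine treatment emergence, and it has no rule based on a report date. Section 10.2 uses *reported* loosely elsewhere, for example for placing TEAEs in a table category. The schedule shows no planned contact for completers between Week 12 and the safety visit, so the literal rule would nearly empty the post-dose rows that the SAP sets up. This stands: the sentence is loose wording that conflicts with its neighbour, and events are lost only on a literal reading.

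A reader might also infer that onsets on post-dose days 15 to 19 are wrongly left out. A visit at day 19 leaves 5 of 19 post-dose days (26%) untabulated, but a visit at the nominal day 14 leaves none. A fixed 14-day window gives every participant the same post-dose period, whereas extending it to the visit would make that period vary with the visit date. The fixed window is a defensible choice, and later events are still listed.

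On the Day 84 cut, it is fair to say that early discontinuers already use the last dosing day, that the post-dose side depends on who counts as a completer, and that the rule is the same in all arms of a descriptive safety analysis. These points limit the size. They do not remove the gap at Days 85 and 86.

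**Conclusion.** Both faults are real and minor.

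The Day 84 boundary misplaces up to 2 on-drug days per completer with a last dose on Day 85 or 86. It misplaces up to 5 post-dose days with a last dose on Days 79 to 83, if such a participant is a completer. These sizes assume that the last dose is taken at the Week 12 visit and that the visit is within its window. Only the by-period and by-onset tables change. Overall TEAE counts do not, so the boundary gives no ground for saying that events are undercounted.

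The two TEAE sentences contradict each other as written, but the surrounding text shows that onset was meant. Applied literally, the second sentence could lower the overall TEAE counts. The documents give no adverse event rate from which to size that.

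**What to change.** Make three wording changes in SAP 10.2:

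1. End the Intervention Period at the actual last dose date for every participant, and start the Safety Follow-up Period the day after.
2. In the time-of-onset table, run *Weeks 9 to 12* from Day 57 to last dose, with *After last dose* following it, for completers as well as early discontinuers.
3. Word the exclusion as AEs with onset more than 14 days after the last dose date. Replacing *reported* with *with onset* alone is not enough, because both sentences would still claim day 14.

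Keep the 14-day TEAE window. No new data are needed: SAP 10.1.1 already uses the date of last dose to compute duration of exposure. The cost is a short text edit and the matching programming of two tables.
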